Vital Signs including orthostatic vital signs, 12-lead ECG, Body Temperature ⁵	X	X	X	X	X	X	X			X
12-Lead Telemetry ⁶			X	X		X	X			
Hematology, Clinical Chemistry, HbA1c, and Urinalysis ⁷	X	X	X	X	X		X			X
Thyroid Panel ⁸	X	X			X		X			X
Coagulation Tests	X	X					X			
Drug Screening, Alcohol Breath, and Urine Cotinine Test	X	X								
COVID-19 PCR	X	X								
Virus Serology	X									
Study Drug Administration			X	X	X	X				
PK Blood Sampling ⁹			X	X	X	X	X	X	X	
FSH Test in Post-Menopausal Participants ¹⁰	X									
Pregnancy Test ¹¹	X	X					X			
C-SSRS	X	X					X			
Adverse Events							Continuously			
Outpatient Visits	X							X	X	X
Residence in Clinic					X					

D=day; ECG=electrocardiogram; PK=pharmacokinetic

1. Follow-up examination will take place 7 days after the last dose, on Day 19 or between Day 19 and Day 22.
2. Discharge after completion of all study 36-hour post-Day 12 dose assessments.
3. Continuous eligibility assessments on Day -1 and Day 1 prior to dosing.
4. Including sex, date of birth, race, and ethnicity.
5. Will take place at Screening, at admission on Day -1, on Day 1 pre-dose (up to 60 minutes pre-dose) and 1 (± 20 min), 2 (± 20 min), 4 (± 20 min), 6 (± 60 min), 8 (± 60 min), 12 (± 60 min); on Days 2-11 on pre-dose (up to 60 minutes pre-dose) and 4 (± 20 min) hours post-dose; on Day 12, pre-dose (up to 60 minutes pre-dose) and 1 (± 20 min), 2 (± 20 min), 4 (± 20 min), and 8 (± 60 min) hours post-dose; on Day 13 (in the morning); and at Follow-up. Orthostatic vital signs will be measured at Screening and at admission on Day -1 only.
6. Will be started on Day 1 and Day 12: approximately 1-2 hours pre-dose and will be continued to approximately 24 hours post-dose.
7. Will be performed at Screening (in fasted state, i.e., participants should fast for 4 hours prior to sample collection), Day -1 (in fasted state), on Day 1 at 8 hours post-dose (in not fasted state) and on Days 2, 6, 13 (in fasted state), and Follow-up (in fasted state). HbA1c will be performed at Screening.
8. A thyroid panel (TSH, FT3, and FT4) will be performed at Screening, on Day -1, on Day 6, Day 13, and at the Follow-up Visit.
9. Will take place:
 - on Day 1: pre-dose (within 2 hours of dosing) and 0.25 (± 2 min), 0.5 (± 2 min), 1 (± 5 min), 1.5 (± 5 min), 2 (± 5 min), 3 (± 10 min), 4 (± 10 min), 6 (± 10 min), 8 (± 10 min), 12 (± 10 min), and 16 (± 30 min) hours post-Day 1 dose,
 - on Day 2: at 24 hours (± 30 min) and 36 hours (± 30 min) post-Day 1 dose,

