7.1.1 Part 1a (SAD)

After assessing eligibility during a 4-week screening period, approximately 40 healthy participants will participate in Part 1a. Each eligible participant will be assigned to 1 of 5 cohorts (8 participants per cohort) to evaluate a total of up to 5 single ascending dose levels. Proposed dose levels are:

Cohort 1: 5 mg

Cohort 2: 10 mg

Cohort 3: 20 mg

Cohort 4: 40 mg

Cohort 5: 80 mg

The starting dose will be 5 mg. Following completion of each ascending dose level, an SRC will review the safety and tolerability data through the follow-up visit of a minimum of 6 evaluable participants. The SRC will also review PK data for up to 48 hours post-dose in at least 6 evaluable participants in order to make decisions whether to escalate to the next planned dose level, decrease the next dose level, repeat a dose level, or to not evaluate any additional dose. The determination of the highest dose level for this study will be based on emerging safety/tolerability and PK data, as recommended by the SRC, but will not exceed the maximum dose currently outlined in the protocol.

For each dose level, 6 participants will receive ATH-399A and 2 participants will receive placebo. Each cohort will utilize sentinel dosing, with one participant receiving ATH-399A and one participant receiving placebo. Provided no clinically significant safety issues are noted in the 48 hours after dosing the initial 2 participants in the cohort, the 6 remaining participants in the cohort will be dosed. Before dosing the rest of the cohort, the Investigator will initiate a discussion via e-mail with the Sponsor's Medical Monitor (MM) or representative to review the available safety and tolerability data of the sentinel participants in order to make a decision regarding continuation of the study with the remaining 6 non-sentinel participants. In the case of

clinically significant safety issues or a sentinel stopping rule is present, then an ad hoc SRC meeting and/or a MM call can be necessary.

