7.1.3 Part 2 (MAD)

Part 2 is the MAD part of the study. After assessing eligibility during the 4-week screening period, approximately 16 participants (with a minimum of 2 of each gender per dose level cohort) will be enrolled in 2 sequential cohorts. Eligible participants in each cohort will come to the clinical unit on the day before the first study drug administration (Day -1), for baseline assessments and to confirm eligibility and will stay in the clinical unit for 14 days (13 nights), from Day -1 until Day 13. Participants will return to the clinical unit for outpatient PK blood sample collections on Day 15 (72 hours post-last dose), and Day 16 (96 hours post-last dose) as well as an outpatient follow-up visit that will take place 7 days after receiving the last dose of study drug, on Day 19 (between Day 19 and Day 22).

Each cohort will include 8 participants, 6 participants will receive ATH-399A and 2 participants will receive placebo. Dose levels of ATH-399A will be based on data from Part 1 (Part 1a and 1b) and recommendation from the SRC. Additionally, [REDACTED]

[REDACTED]

[REDACTED]

[REDACTED]

From Day 1 to Day 12, participants will receive either ATH-399A or placebo once daily (QD) for a total of twelve (12) consecutive days. On Days 1 and 12, participants will fast for a minimum of 10 hours prior to dosing and 4 hours following dosing. From Days 2 to 11, participants will fast for a minimum of 2 hours prior to dosing and 2 hours following dosing.

Following completion of each dose level (both cohorts), an SRC will review the safety and tolerability data through the follow-up visit of a minimum of 6 evaluable participants. The SRC will also review PK data for up to 24 hours post-last dose in at least 6 evaluable participants in

order to make decisions whether to escalate to the next planned dose level, decrease the next dose level, repeat a dose level, or to not evaluate any additional dose. The time interval when escalating the dose from the first dosing of Cohort 1 of the MAD to the first dosing of Cohort 2 of the MAD will be approximately 3.5 weeks.

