9.7 Assignment to Study Treatment

Participants will be assigned sequentially to study part and cohort, and randomized within their assigned part/cohort of the study. Participants will be numbered during screening and study procedures according to the site SOP.

For each cohort in Parts 1a, 1b and 2, eligible participants for participation will be randomized (on Day 1) to receive either the active or placebo. Participants in Part 1a and Part 2 will be randomized in a 3:1 ratio, for a total of 6 participants per cohort receiving ATH-399A and 2 participants receiving the placebo in each dose level. In Part 1a, two sentinel participants will be dosed initially (1 active and 1 placebo). The remaining 6 participants (5 actives and 1 placebo) will be dosed at least 48 hours later after sentinels have been evaluated. Participants in Part 1b will be randomized in one of the 2 arms to receive study treatments in the sequence AB or BA. If PK data analyzed from Parts 1a and 1b demonstrate a potential accumulation of ATH-399A, a sentinel approach similarly used in Part 1a will be considered for the dosing of Part 2 where sentinels will be dosed on Day 1 and the remaining participants will be dosed at least 96 hours later, which would allow safety assessment of the sentinel subjects after steady-state has been attained. One randomization scheme will be produced for each cohort separately.

Participants may be automatically replaced if they withdraw/discontinue after randomization but prior to any dosing. Replacement of participants who withdraw/discontinue post dose will be at the discretion of the Sponsor. Procedures will be performed according to the site's SOP.

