3.3 Treatment Assignment

3.3.1 Part 1a (SAD)

Participants allocated to the SAD part will receive a single dose of ATH-399A, or matching placebo, under fasting conditions. The planned dose levels and regimens are listed in Table 3.3-1, below.

Table 3.3-1: SAD Treatments

Cohort Number	Number of Participants Receiving ATH-399A	Number of Participants Receiving Placebo	Planned Dose
1	6 (1 sentinel, 5 non-sentinel)	2 (1 sentinel, 1 non-sentinel)	5 mg
2	6 (1 sentinel, 5 non-sentinel)	2 (1 sentinel, 1 non-sentinel)	10 mg
3	6 (1 sentinel, 5 non-sentinel)	2 (1 sentinel, 1 non-sentinel)	20 mg
4	6 (1 sentinel, 5 non-sentinel)	2 (1 sentinel, 1 non-sentinel)	40 mg
5	6 (1 sentinel, 5 non-sentinel)	2 (1 sentinel, 1 non-sentinel)	80 mg

For each dose level, 6 participants will receive ATH-399A and 2 participants will receive placebo. Each cohort will utilize sentinel dosing, with one participant receiving ATH-399A and one participant receiving placebo. For Cohorts 1-3, provided no clinically significant safety issues are noted in the 48 hours after dosing the initial 2 participants in the cohort, the 6 remaining participants in the cohort will be dosed. For Cohorts 4 and 5, provided no clinically significant safety issues are noted in the 96 hours after dosing the initial 2 participants in the cohort, the 6 remaining participants in the cohort will be dosed.

This document is confidential.

[figure not shown]
The SRC will consider the data on a cohort basis, but also on the basis of cumulative information across cohorts as the study progresses. All dose levels will be considered completed following SRC approval.

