3.4 Randomization

Randomization schemes will be generated using SAS® for Windows software, prior to study execution. Block randomization will be used, and one randomization scheme will be produced for each cohort separately.

Participants will be randomized to treatments on Day 1. For Parts 1a and 2 (SAD and MAD, respectively), participants will be randomized 6:2 to active:placebo. In Parts 1a and 2, the first two participants in each cohort will be sentinel participants and will be randomized 1:1 to active:placebo. For Part 1b (food effect) participants will be randomized to 1 of 2 ATH-399A treatment condition sequences (AB or BA).

Each participant will be randomly assigned a 5-digit randomization number. For Part 1a, they will begin with “11” and “12” for Cohorts 1 and 2, respectively. For Part 1b, they will begin with “10”. For Part 2, they will begin with “21” and “22” for Cohorts 1 and 2, respectively. For Parts 1a and 2, these numbering systems will be continued for each cohort until all cohorts are enrolled. Each randomization number corresponds to a treatment assignment on the randomization scheme. For Part 1a, sentinel participants will be assigned to the first 2 randomization numbers of their cohort (i.e., 11001, 11002 for Cohort 1, and 12001, 12002 for Cohort 2). For Part 2, sentinel participants will also be assigned to the first 2 randomization numbers of their cohort (i.e., 21001, 21002 for Cohort 1, 22001, 22002 for Cohort 2, and 23001, 23002 for Cohort 3).

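### SAP and Protocol state different sentinel rules: 96 h against 48 h for the 40 and 80 mg single-dose cohorts, and unconditional against conditional sentinels in Part 2

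*SAP*

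**What the plan says.** **Part 1a.** Protocol 7.1.1, with the same rule in the Synopsis, makes no distinction between cohorts: "Provided no clinically significant safety issues are noted in the 48 hours after dosing the initial 2 participants in the cohort", the other six are dosed. Protocol 9.7 words it as a minimum: the six "will be dosed at least 48 hours later after sentinels have been evaluated". SAP 3.3.1 keeps 48 hours for Cohorts 1 to 3 but then states: "For Cohorts 4 and 5, provided no clinically significant safety issues are noted in the 96 hours after dosing the initial 2 participants", the rest are dosed.

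**Part 2.** In Protocol 9.7, if PK from Parts 1a and 1b suggests accumulation, "a sentinel approach similarly used in Part 1a will be considered for the dosing of Part 2". The gap would then be at least 96 hours, "which would allow safety assessment of the sentinel subjects after steady-state has been attained". Protocol 9.8 mentions 1:1 sentinel randomisation for Part 1a only. SAP 3.4 sets no condition: "In Parts 1a and 2, the first two participants in each cohort will be sentinel participants and will be randomized 1:1 to active:placebo". It reserves the first two randomisation numbers of Cohorts 1, 2 and 3 for them. SAP Table 3.3-2 shows 6 active and 2 placebo per cohort with no sentinel split, unlike Table 3.3-1 for Part 1a, and the SAP states no hold length for Part 2.

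SAP Section 11, which concerns analyses, reports no change from the Protocol, and no other section of the SAP flags one.

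**The concern.** The sentinel step limits how many people are exposed before anyone has looked at the first active participant at a dose. In a first-in-human study this matters most at the two highest single doses and at the start of repeat dosing. Site staff following the Protocol and a statistician following the SAP could each comply with their own document and still apply different rules: a different waiting time at 40 and 80 mg, and a Part 2 scheme built with or without a 1:1 sentinel pair. A second question is whether the assessment schedules and the stated interval between Part 2 cohorts fit a 96-hour hold, if one is used.

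**Working it through.** **1. The rules side by side**

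| | Protocol | SAP |
|---|---|---|
| Part 1a, Cohorts 1–3 | 48 h (Synopsis, 7.1.1); at least 48 h (9.7) | 48 h (3.3.1) |
| Part 1a, Cohorts 4–5 | the same | 96 h (3.3.1) |
| Part 2, sentinels used? | considered if Part 1 PK suggests accumulation (9.7) | yes, every cohort (3.4); no split in Table 3.3-2 |
| Part 2, pair randomised 1:1? | 9.8 names Part 1a only | yes (3.4) |
| Part 2, hold | at least 96 h, if used (9.7) | not stated |

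Size in Part 1a: 96/48 = 2. Non-sentinel ATH-399A participants affected: 2 cohorts × 5 = 10.

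**2. Does the Part 2 scheme depend on the rule?** The totals stay 6:2 either way, but the order does not. With one block of 8 and no sentinel pair, the chance that the first two participants are one active and one placebo is 2 × (6/8) × (2/7) = 24/56 = 0.43. With blocks of 4 it is 2 × (3/4) × (1/3) = 0.50. Block size is not stated, so both are shown. A scheme built without the pair therefore cannot be relied on to supply one later.

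**3. Scheduled assessments after 48 h and up to 96 h**

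| | Part 1a (Table 1) | Part 2 (Table 3) |
|---|---|---|
| Vital signs and ECG | 0 (last at 48 h) | 4 (52, 72, 76, 96 h) |
| Telemetry | 0 (ends about 48 h) | 0 (ends about 24 h after the Day 1 dose) |
| Safety labs | 0 (Day 3, then follow-up) | 0 |
| PK blood | 2 (72 and 96 h) | 0 (36 h, then Day 9) |
| Adverse events | continuous | continuous |

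Part 2 labs are taken "on Day 1 at 8 hours post-dose (in not fasted state) and on Days 2, 6, 13 (in fasted state") and at follow-up. Ninety-six hours after the first dose is Day 5. Day 6 is (6 − 1) × 24 = 120 h.

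**4. Calendar, Part 2.** Protocol 7.1.3 gives the interval from the first dosing of Cohort 1 "to the first dosing of Cohort 2 of the MAD will be approximately 3.5 weeks", which is 3.5 × 7 = 24.5 days. This cannot be rebuilt exactly because the time needed for Safety Review Committee (SRC) review is not stated. Days from the cohort's first dose to the required data = (study day − 1) + hold/24; margin = 24.5 − that figure.

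| Data required | No hold | 96 h hold |
|---|---|---|
| Follow-up, Day 19 | 18 days, margin 6.5 | 22 days, margin 2.5 |
| Follow-up, Day 22 | 21 days, margin 3.5 | 25 days, margin −0.5 |
| 24 h after last dose (Day 13) | 12 days, margin 12.5 | 16 days, margin 8.5 |

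The first two rows use the requirement in Protocol 7.1.3 for safety data through follow-up. The third uses the earlier data cut in Protocol 13.1.5.1. Under 7.1.3 the SRC needs at least 6 evaluable participants, so at least 6 − 2 = 4 non-sentinels must reach the visit, and a hold does move the review date.

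**5. Calendar, Part 1a.** Non-sentinel follow-up (Day 8 to Day 11) falls 9 to 12 days after the sentinel dose with 48 h and 11 to 14 days with 96 h. No interval between Part 1a cohorts is stated, so there is nothing to compare this with.

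**The case against.** The best defence is that the texts can be read together. Protocol 9.7 sets a minimum, which a 96-hour hold satisfies, and the SAP's figure is the longer one. In Part 2, numbers could be reserved for a sentinel pair and the hold applied only if PK calls for it. SAP section 3 is study description, and the Protocol governs conduct. The SAP cites Protocol Amendment III. The version pages are not in the text reviewed here, so a simple version mismatch cannot be confirmed or excluded.

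Part of this stands. Compatibility with 9.7 is real, but the Synopsis and 7.1.1 release every cohort on a 48-hour observation. Permitting 96 hours is not the same as requiring it. The Part 2 reading is workable, but neither document states it, and Protocol 9.8 points the other way.

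Several stronger readings are tempting and should not be drawn:

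- *That no 96-hour hold has safety assessments behind it.* In Part 2 participants are resident, with vital signs and ECG before dosing and 4 hours after it on Days 2 to 11. The gap there is in labs, telemetry and PK.
- *That four of the ten criteria in Protocol 10.1 (liver, AUC, creatinine, hematology) lack late data at release.* The creatinine and hematology criteria each need two ATH-399A participants, and a 1:1 pair has one. AUC over 24 hours is covered by Day 1 sampling. Liver tests remain, last drawn on Day 2 if release is at exactly 96 hours. The hold is a minimum, so a release after the Day 6 labs would also comply.
- *That the Protocol claims to confirm steady state by PK before release.* It says only that safety can be assessed once steady state is reached.
- *That the 3.5-week interval is impossible.* The figure is approximate, the margin is negative only at the end of the follow-up window, and Protocol 13.1.5.1 gives an earlier data cut. The interval may also describe a cohort without a stagger, since the Protocol makes the stagger conditional.

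**Conclusion.** Two contradictions hold and need correcting. For the 40 and 80 mg cohorts of Part 1a the hold is 48 hours in the Protocol Synopsis and 7.1.1 and 96 hours in the SAP, which changes when 10 ATH-399A participants are dosed. In Part 2, sentinels are conditional in the Protocol and unconditional in the SAP, which changes how the scheme must be generated. Both follow from the wording alone and need no assumption beyond the supplied texts being the current ones.

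The remaining points are supporting. If 96 hours is meant in Part 1a, the extra 48 hours bring PK samples and adverse-event reports but no scheduled vital signs, ECG, telemetry or labs. In Part 2, no labs fall between Day 2 and Day 6 and no PK sample between 36 hours and Day 9, which sits awkwardly with the steady-state rationale. If a 4-day stagger is used and review waits for follow-up, the margin falls from between 6.5 and 3.5 days to between 2.5 and −0.5 days: tight, not unworkable.

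**What to change.** Reconcile the Protocol Synopsis, 7.1.1, 9.7 and 9.8 with SAP 3.3.1, 3.3.3 (including Table 3.3-2) and 3.4, so that one Part 1a hold per cohort and one Part 2 sentinel policy appear in every place. If the Part 2 policy is conditional, both documents should say so and state the hold. Generate the Part 2 randomisation scheme to match. Then check that Tables 1 and 3, the steady-state rationale in 9.7 and the 3.5-week interval in 7.1.3 agree with the hold the sponsor chooses, and state which data cut (7.1.3 or 13.1.5.1) governs SRC review.

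The choice of hold, and of any assessments tied to it, belongs to the sponsor and investigator. The cost is mainly wording in a protocol amendment and a SAP revision. Any change to the schedule or the interval would depend on the hold chosen.

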3.3.2 Part 1b (Food Effect)

Participants allocated to the food effect part will be randomized to one of the 2 sequences, AB or BA, and will receive the following study treatments in each period:

- **Treatment A:** Single dose of ATH-399A after a high-calorie, high-fat breakfast.
- **Treatment B:** Single dose of ATH-399A after fasting.

For treatment A, participants will complete a supervised fast of at least 10 hours before their meal. Drug administration will occur approximately 30 minutes after the meal has been started. For treatment B, participants will fast for at least 10 hours before until at least 4 hours after dosing. Selection of the dose to be administered in Part 1b will depend on the results of Part 1a.

[figure not shown]
3.3.3 Part 2 (MAD)

Participants allocated to the MAD part will receive daily doses of ATH-399A, or matching placebo, under fasting conditions, for 12 consecutive days. The planned dose levels and regimens are listed below in Table 3.3-2.

Table 3.3-2: MAD Treatments

Cohort Number	Number of Participants Receiving ATH-399A	Number of Participants Receiving Placebo	Planned Dose
1	6	2	TBD mg
2	6	2	TBD mg
3	6	2	TBD mg

Each cohort will include 8 participants, 6 participants will receive ATH-399A and 2 participants will receive placebo.

Dose levels of ATH-399A will be based on data from Part 1 (Part 1a and 1b) and recommendation from the SRC. From Day 1 to Day 12, participants will receive either ATH-399A or placebo once daily (QD) for a total of twelve (12) consecutive days.

This document is confidential.

3.4 Randomization

Randomization schemes will be generated using SAS® for Windows software, prior to study execution. Block randomization will be used, and one randomization scheme will be produced for each cohort separately.

Participants will be randomized to treatments on Day 1. For Parts 1a and 2 (SAD and MAD, respectively), participants will be randomized 6:2 to active:placebo. In Parts 1a and 2, the first two participants in each cohort will be sentinel participants and will be randomized 1:1 to active:placebo. For Part 1b (food effect) participants will be randomized to 1 of 2 ATH-399A treatment condition sequences (AB or BA).

Each participant will be randomly assigned a 5-digit randomization number. For Part 1a, they will begin with “11” and “12” for Cohorts 1 and 2, respectively. For Part 1b, they will begin with “10”. For Part 2, they will begin with “21” and “22” for Cohorts 1 and 2, respectively. For Parts 1a and 2, these numbering systems will be continued for each cohort until all cohorts are enrolled. Each randomization number corresponds to a treatment assignment on the randomization scheme. For Part 1a, sentinel participants will be assigned to the first 2 randomization numbers of their cohort (i.e., 11001, 11002 for Cohort 1, and 12001, 12002 for Cohort 2). For Part 2, sentinel participants will also be assigned to the first 2 randomization numbers of their cohort (i.e., 21001, 21002 for Cohort 1, 22001, 22002 for Cohort 2, and 23001, 23002 for Cohort 3).

3.5 Blinding

This is a randomized study using active drug (ATH-399A) and placebo control. Parts 1a and 2 are double-blind, while part 1b is randomized and open-label. Randomization to treatment group will be performed after participants have been deemed eligible for study participation. Blinding will be used in Parts 1a and 2 to reduce potential bias during data collection and evaluation of clinical endpoints. The participants and the clinical personnel involved in the collection, monitoring, revision, or evaluation of adverse events (AEs), or personnel who could have an impact on the outcome of the study will be blinded with respect to the participant’s treatment assignment (active or placebo). Blinding will be maintained until at least the clinical phase of the study is completed, i.e., when reporting and evaluation of all AEs have been completed for all cohorts.

Blinded PK results will be available during the course of the study. These results will be reported without revealing the participant’s identity.

